10.8. Body Mass Index (BMI) Calculation

The BMI is calculated using metric units with the formula provided below: The Takeda standard for collecting height is centimeters without decimal places and for weight it is kilograms (kg) with 1 decimal place. BMI should be derived as:

Metric:
$$\text{BMI} = \text{weight (kg)} / \text{height (m)}^2 [\text{optional}]$$

Note that although height is reported in centimeters, the formula uses meters for height; meters can be determined from centimeters by dividing by 100. Thus, for example, if height=176 cm (1.76 meters) and weight=79.2 kg, then $\text{BMI} = 79.2 / 1.76^2 = 25.56818 \text{ kg/m}^2$. The values should be reported to 1 decimal place by rounding. Thus, in the above example BMI would be reported as 25.6 kg/m². As the BMI is used as entry criteria based on >25kg/m² cut-off point, then this determination must be made after rounding.

10.9. Documentation of Medical history, Concurrent Medical Conditions and comorbidities

Medical history is history of diseases indicated before signing of the Informed Consent Form.

Concurrent medical conditions are those significant ongoing conditions or diseases that are present at signing of informed consent.

Comorbidities (concomitant disease) are diseases which occur after start of Edarbi® treatment and are not related to the Edarbi® treatment. Comorbidities may include not limited to cardiovascular disorders (coronary artery disease, peripheral artery disease, cerebrovascular disease), diabetes, chronic pulmonary artery disease, chronic kidney disease. The condition (ie, diagnosis) should be described.

Risk factors are conditions which increase probability of cardiovascular disease in patients with HTN at the moment of signing ICF. Risk factors are described in accordance with Russian guidelines “Diagnostics and treatment of hypertension” (2010) [21].

Time of medical event/disease	How it should be documented
Birth to day before ICF signed	Medical history
At the moment of ICF signing	Risk factors
At the moment of ICF signing	Concurrent medical conditions
After ICF signing and start of Edarbi® treatment	Adverse Events

11 Safety Reporting

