10.2. Data collection overview

The documentation of study data will be reported by the attending physician via paper or electronic case report form (CRF).

Term	Baseline visit (V1)	Observational visit (V2)	Observational visit (V3)	Final Observational visit (V4)
Inclusion/exclusion criteria	X			
Signed Informed consent form	X			
Date of visit	X	X	X	X
Demographic information	X			
Medical history (incl. risk factors, prior diseases, prior HTN therapy etc)	X			
Body Mass Index (BMI)	X	X	X	X
Physical examination and vital signs*	X	X	X	X
HTN therapy (drugs, doses)	X	X	X	X

Laboratory tests and instrumental exams*	X	X	X	X
Concurrent medical conditions	X			
Concomitant medication		X	X	X
Adverse events		X	X	X

* All examinations (physical examination and vital signs, laboratory tests and instrumental exams) are done in accordance with clinical routine practice and physician's decision. Instrumental exams are measurement of blood pressure, heart rate, ECG, 24-hour ambulatory blood pressure monitoring. All examinations should be registered in the CRF only if they are done in routine practice.

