10.3. Data collected on the Baseline visit

Baseline visit is a visit after physician makes a decision to prescribe Edarbi® for HTN treatment. It means that investigator inform patient about the study only after taking decision about strategy of HTN treatment.

Data to be collected:

- Date of visit (day, month, year)
- Date of Informed consent form signing (day, month, year)
- Compliance with Inclusion/exclusion criteria
- Demographic information: sex, date of birth, ethnicity, region of residence (city, town etc)
- Medical history:
 - History of HTN
 - Duration of HTN/first diagnosed
 - Presence of HTN target organ damage
 - Risk factors of cardiovascular disease (smoking, dyslipidaemia, glucose intolerance, obesity, abdominal obesity, family history of cardiovascular disease,)
 - Cardiovascular diseases history:
 - established cardiovascular diseases (coronary artery disease, chronic heart failure, arrhythmias, peripheral artery diseases, ischemic heart disease etc.)
 - history of cardiovascular events (myocardial infarction, stroke, etc.)
 - Alcohol use
- Diagnose of HTN: grade, stage, risk.
- Physical examination and vital signs: height (cm), weight (kg), waist circumference (cm), body mass index, systolic and diastolic blood pressure (position, time, values), heart rate, physical inactivity

- HTN treatment:
 - previous HNT-treatment (if applicable),
 - reason(s) for discontinuation of previous HNT-treatment (if applicable),
 - monotherapy/combination treatment,
 - Edarbi® dosage regimen,
 - other HTN co-medications: INN, trade name, dosage regimen (if applicable).
- Laboratory data (last available measurements, if done within routine practice):
 - total cholesterol,
 - triglycerides,
 - low-density lipoproteins,
 - high-density lipoproteins,
 - blood glucose,
 - serum creatinine,
 - urea,
 - glycated haemoglobin
- Concurrent medical conditions (diabetes mellitus, chronic kidney disease, chronic obstructive pulmonary disease, etc.)
- Concomitant medication: INN, trade name, dosage regimen (single and total daily dose), duration of treatment, indication for administration
- Adverse events: seriousness, severity, causality, start and stop dates, action, outcomes

10.4. Data collected on the Observational visits 2, 3 and 4

Data to be collected:

- Date of visit (day, month, year)
- Diagnose of HTN: grade, stage, risk.

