- Physical examination and vital signs: height (cm), weight (kg), waist circumference (cm), body mass index, systolic and diastolic blood pressure (position, time, values), heart rate
- HTN treatment:
 - monotherapy/combination treatment,
 - Edarbi® dosage regimen,
 - other HTN co-medications: INN, trade name, dosage regimen.
- Laboratory data (last available measurements, if done within routine practice):
 - total cholesterol
 - triglycerides,

- low-density lipoproteins,
- high-density lipoproteins,
- blood glucose,
- serum creatinine,
- urea,
- glycated haemoglobin.
- Concomitant diseases
- Concomitant medication: INN, trade name, dosage regimen (single and total daily dose), duration of treatment, indication for administration
- Adverse events: seriousness, severity, causality, start and stop dates, action, outcomes

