11.1 Definitions

11.1.1. Adverse Event

An Adverse Event (AE) is defined as any untoward medical occurrence in a patient administered a drug; it does not necessarily have to have a causal relationship with this treatment.

An AE can therefore be any unfavorable and unintended sign (eg, a clinically significant abnormal laboratory finding), symptom, or disease temporally associated with the use of a drug whether or not it is considered related to the drug.

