11.1.2. Additional Points to Consider for AEs

An untoward finding generally may:

- Indicate a new diagnosis or unexpected worsening of a pre-existing condition. (Intermittent events for pre-existing conditions underlying disease should not be considered AEs.)
- Necessitate therapeutic intervention.
- Require an invasive diagnostic procedure.
- Require discontinuation or a change in dose of study medication or a concomitant medication.
- Be considered unfavorable by the investigator for any reason.

Diagnoses vs signs and symptoms:

- Each event should be recorded to represent a single diagnosis. Accompanying signs (including abnormal laboratory values or ECG findings) or symptoms should NOT be recorded as additional AEs. If a diagnosis is unknown, sign(s) or symptom(s) should be recorded appropriately as an AE(s).

Laboratory values and ECG findings:

- Changes in laboratory values or ECG parameters are only considered to be AEs if they are judged to be clinically significant (ie, if some action or intervention is required or if the investigator judges the change to be beyond the range of normal physiologic fluctuation). A laboratory re-test and/or continued monitoring of an abnormal value are not considered an intervention. In addition, repeated or additional noninvasive testing for verification, evaluation or monitoring of an abnormality is not considered an intervention.
- If abnormal laboratory values or ECG findings are the result of pathology for which there is an overall diagnosis (eg, increased creatinine in renal failure), the diagnosis only should be reported appropriately as an AE.

Pre-existing conditions:

- Pre-existing conditions (present at the time of signing of informed consent) are considered concurrent medical conditions and should NOT be recorded as AEs. However, if the patient experiences a worsening or complication of such a concurrent condition, the worsening or complication should be recorded as an AE (worsening or complication occurs after start of study medication). Investigators should ensure that the event term recorded captures the change in the condition (eg, “worsening of...”).
- If a patient has a pre-existing episodic condition (eg, asthma, epilepsy) any occurrence of an episode should only be captured as a AE if the episodes become more frequent, serious or severe in nature, that is, investigators should ensure that the AE term recorded captures the change in the condition from Baseline (eg “worsening of...”).

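### Protocol 10.9 and SAP 7 define comorbidities as unrelated diseases arising after Edarbi start, which conflicts with the AE rules and leaves a baseline item in SAP 9.2 that cannot be filled as defined

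*Protocol*

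**What the plan says.** Protocol 10.9 separates diseases by when they occur. Those present at consent are concurrent medical conditions. For later ones it says: "Comorbidities (concomitant disease) are diseases which occur after start of Edarbi® treatment and are not related to the Edarbi® treatment". It gives examples, among them coronary and peripheral artery disease, diabetes and chronic kidney disease, and asks for the diagnosis to be described. SAP 7 repeats the definition.

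The table that closes 10.9, also repeated in SAP 7, has one row for what happens later, "After ICF signing and start of Edarbi® treatment", and assigns it to Adverse Events. It sets no causality condition and has no row for comorbidities.

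Protocol 10.4 lists, for Visits 2 to 4, "Concomitant diseases" and, as a separate item, "Adverse events: seriousness, severity, causality, start and stop dates, action, outcomes". The schedule in Protocol 10.2 has no concomitant-disease row at those visits. Its row "Concurrent medical conditions" is marked at Visit 1 only.

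Protocol 11.1.1 says of an adverse event that "it does not necessarily have to have a causal relationship with this treatment". Protocol 11.1.5 provides Not Related as a category of AE, and the form described in 11.2.2 records that judgement. Protocol 11.1.2 sets the one stated limit: "Pre-existing conditions (present at the time of signing of informed consent) are considered concurrent medical conditions and should NOT be recorded as AEs". Worsening of such a condition after treatment start is still an AE.

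SAP 9.2 item 6 lists comorbidities among the patient characteristics to be described before Edarbi is started.

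**The concern.** Incidence and type of adverse events is the only safety outcome, and the study has no control group against which incomplete recording might show. The comorbidity definition asks the investigator to judge causality first and then gives the unrelated disease a name other than adverse event. Protocol 10.4 supplies a data item under that name. A site could reasonably read the two together as a place to put an unrelated new diagnosis in place of the AE form. Such an entry would miss the tables of all AEs in Protocol 13.2.3 and SAP 10. Tables of adverse drug reactions, if limited to related events, would not change.

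The second matter is one of programming. A baseline table is specified with a term that the same SAP reserves for events after baseline.

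**Working it through.** No figure in the plan is at issue, so the check is to follow one case through the text. Take diabetes, one of 10.9's own examples, first diagnosed after Edarbi start and judged unrelated.

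| Source | Classification of the case |
|---|---|
| Protocol 10.9 and SAP 7, definition | Comorbidity (concomitant disease) |
| Protocol 10.4 | Fits the separate concomitant-disease item |
| Protocol 10.2 | No concomitant-disease row at Visits 2 to 4; the AE row applies |
| Protocol 10.9 and SAP 7, table | Adverse event |
| Protocol 11.1.1 | Adverse event; relatedness is irrelevant |
| Protocol 11.1.2 | A new diagnosis is an untoward finding |
| Protocol 11.1.5 | Adverse event, Not Related |
| Protocol 11.2.3 | Within the AE collection period |

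The case is a comorbidity and an adverse event at once. Recording it in both places satisfies every passage. Recording it only as a concomitant disease satisfies the definition and 10.4, but breaks the 10.9 table and section 11.

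Next, what happens to an entry made only as a concomitant disease:

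- Protocol 12.3.4 names adverse events, medical history and concurrent medical conditions for MedDRA coding. Comorbidities are not named.
- SAP 7 names medical history, risk factors, concurrent medical conditions and adverse events for summary. Comorbidities are not named.
- Protocol 13.2 and SAP 3 promise descriptive analysis of all collected data. That could produce a listing of the entry but would not place it in the AE tables.

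The possible effect is one-sided. All-causality AE counts can be too low by this route, not too high. If every site follows the 10.9 table, the loss is zero. The documents give no AE rate and no share of misplaced entries, so no upper figure can be derived.

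Finally, SAP 9.2 item 6. A comorbidity under SAP 7 has its onset after treatment start, whereas item 6 requires presence before treatment start. No disease meets both conditions. The diseases that item 6 presumably intends are collected at Visit 1, but under two parts of Protocol 10.3:

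- coronary and peripheral artery disease, and past events such as infarction and stroke, are under the cardiovascular part of medical history;
- diabetes, chronic kidney disease and chronic obstructive pulmonary disease are under "Concurrent medical conditions (diabetes mellitus, chronic kidney disease, chronic obstructive pulmonary disease, etc.)".

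Replacing the word in item 6 with concurrent medical conditions alone could therefore drop established cardiovascular disease from the table.

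**The case against.** The best defence is that the comorbidity sentence only defines a term, while the table beneath it is the documentation rule. That rule has a single post-start destination, Adverse Events. SAP 7 fits this reading, since it plans no separate post-start summary of comorbidities. There are further safeguards: investigators are trained in safety reporting (Protocol 12.1.1), logic checks generate queries (12.1.3), SAP 5 provides for safety reconciliation, and Protocol 13.2.3 and SAP 10 add AEs that reached drug safety but not the study database. Whether the CRF has a concomitant-disease field at all cannot be seen, and the absence of a row in 10.2 makes it less certain. In item 6, the heading fixes the time point, and the share of patients with diabetes is requested there separately, so a sensible programmer would probably use the baseline data.

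Most of this stands, and it limits the claim. A reader might infer that the plan tells sites to leave unrelated diseases off the AE form, or that AE incidence will be understated. Neither is supported: no passage grants an exemption, and dual recording is open to every site. A reader might also infer that serious events are lost. That is not supported either, because 11.1.3 covers any untoward occurrence that meets a seriousness criterion.

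The defence does not remove the conflict. The definition turns on a causality test that the AE rules reject, and 10.4 gives the term its own item. None of the safeguards, as described, compares concomitant-disease entries with AE forms, and the Data Management Plan is not available here. Item 6 still works only if the programmer sets aside SAP 7's definition.

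**Conclusion.** The point holds as a modest correction to the documentation rules. Two conclusions follow.

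1. The comorbidity definition in Protocol 10.9 and SAP 7, together with the separate item in 10.4, conflicts with 11.1.1, 11.1.5 and 10.9's own table. Protocol 10.2 and 10.4 also disagree on whether the item is collected. The consequence is a risk that some unrelated new diseases are recorded only as concomitant diseases and miss the all-causality AE tables. Its size is unknown and may be zero. It rests on two assumptions that the documents do not settle: that the CRF carries the 10.4 item, and that some sites use it in place of the AE form.
2. SAP 9.2 item 6 cannot be met under SAP 7's definition, whatever sites do. Its reach is narrow: one descriptive item, in an SAP whose own analysis is confined to the Kazakhstan data (SAP 2.4 and 4).

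The primary and secondary blood-pressure outcomes are not affected.

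**What to change.** 1. In Protocol 10.9 and SAP 7, delete the definition of comorbidities as unrelated post-start diseases. Alternatively, keep the term and add that a disease with onset after the first Edarbi intake is recorded as an AE whatever its causality. Either way, leave the 11.1.2 handling of pre-existing conditions and their worsening as it is.
2. Make Protocol 10.2 and 10.4 agree on whether concomitant diseases are collected at Visits 2 to 4.
3. In SAP 9.2 item 6, replace comorbidities with diseases present at baseline as collected under Protocol 10.3: concurrent medical conditions plus the established cardiovascular diseases and events in the medical history.
4. Before database lock, if the CRF holds concomitant-disease entries from Visits 2 to 4, list those that match neither a baseline condition nor an AE form, and query only those. If the Data Management Plan already provides this, nothing more is needed.

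The cost is wording in two documents, one listing and a few site queries. Reported AE incidence may rise, and that should be accepted as more complete recording.

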11.1 Definitions

11.1.1. Adverse Event

An Adverse Event (AE) is defined as any untoward medical occurrence in a patient administered a drug; it does not necessarily have to have a causal relationship with this treatment.

An AE can therefore be any unfavorable and unintended sign (eg, a clinically significant abnormal laboratory finding), symptom, or disease temporally associated with the use of a drug whether or not it is considered related to the drug.

11.1.2. Additional Points to Consider for AEs

An untoward finding generally may:

- Indicate a new diagnosis or unexpected worsening of a pre-existing condition. (Intermittent events for pre-existing conditions underlying disease should not be considered AEs.)
- Necessitate therapeutic intervention.
- Require an invasive diagnostic procedure.
- Require discontinuation or a change in dose of study medication or a concomitant medication.
- Be considered unfavorable by the investigator for any reason.

Diagnoses vs signs and symptoms:

- Each event should be recorded to represent a single diagnosis. Accompanying signs (including abnormal laboratory values or ECG findings) or symptoms should NOT be recorded as additional AEs. If a diagnosis is unknown, sign(s) or symptom(s) should be recorded appropriately as an AE(s).

Laboratory values and ECG findings:

- Changes in laboratory values or ECG parameters are only considered to be AEs if they are judged to be clinically significant (ie, if some action or intervention is required or if the investigator judges the change to be beyond the range of normal physiologic fluctuation). A laboratory re-test and/or continued monitoring of an abnormal value are not considered an intervention. In addition, repeated or additional noninvasive testing for verification, evaluation or monitoring of an abnormality is not considered an intervention.
- If abnormal laboratory values or ECG findings are the result of pathology for which there is an overall diagnosis (eg, increased creatinine in renal failure), the diagnosis only should be reported appropriately as an AE.

Pre-existing conditions:

- Pre-existing conditions (present at the time of signing of informed consent) are considered concurrent medical conditions and should NOT be recorded as AEs. However, if the patient experiences a worsening or complication of such a concurrent condition, the worsening or complication should be recorded as an AE (worsening or complication occurs after start of study medication). Investigators should ensure that the event term recorded captures the change in the condition (eg, “worsening of...”).
- If a patient has a pre-existing episodic condition (eg, asthma, epilepsy) any occurrence of an episode should only be captured as a AE if the episodes become more frequent, serious or severe in nature, that is, investigators should ensure that the AE term recorded captures the change in the condition from Baseline (eg “worsening of...”).
- If a patient has a degenerative concurrent condition (eg, cataracts, rheumatoid arthritis), worsening of the condition should only be captured as an AE if occurring to a greater extent to that which would be expected. Again, investigators should ensure that the AE term recorded captures the change in the condition (eg, “worsening of...”).

Worsening of AEs:

- If the patient experiences a worsening or complication of an AE after any change in study medication, the worsening or complication should be recorded as a new AE. Investigators should ensure that the AE term recorded captures the change in the condition (eg, “worsening of...”).

Changes in severity of AEs:

- If the patient experiences changes in severity of an AE, the event should be captured once with the maximum severity recorded.

Preplanned surgeries or procedures:

- Preplanned procedures (surgeries or therapies) that were scheduled prior to signing of informed consent are not considered AEs. However, if a preplanned procedure is performed early (eg, as an emergency) due to a worsening of the pre-existing condition, the worsening of the condition should be captured appropriately as an AE. Complications resulting from any planned surgery should be reported as AEs.

Elective surgeries or procedures:

- Elective procedures performed where there is no change in the patient’s medical condition should not be recorded as AEs. Complications resulting from an elective surgery should be reported as AEs.

Insufficient clinical response (lack of efficacy):

- Insufficient clinical response, efficacy, or pharmacologic action, should NOT be recorded as an AE. The investigator must make the distinction between exacerbation of pre-existing illness and lack of therapeutic efficacy.

11.1.3. Serious AEs

A serious AE (SAE) is any AE which results in death, is life threatening, requires inpatient hospitalisation or prolongation of existing hospitalisation, results in persistent or significant disability or incapacity, or is a congenital anomaly or birth defect.

A serious AE are defined as any untoward medical occurrence that at any dose:

1. Results in DEATH.

2. Is LIFE THREATENING.

The term “life threatening” refers to an event in which the patient was at risk of death at the time of the event; it does not refer to an event that hypothetically might have caused death if it were more severe.

3. Requires inpatient HOSPITALIZATION or prolongation of existing hospitalization.

4. Results in persistent or significant DISABILITY/INCAPACITY.

5. Leads to a CONGENITAL ANOMALY/BIRTH DEFECT.

6. Is an OTHER IMPORTANT MEDICAL EVENT that satisfies any of the following:

- May require intervention to prevent items 1 through 5 above.
- May expose the patient to danger, even though the event is not immediately life threatening or fatal or does not result in hospitalization.
- Includes any event or synonym described in the Takeda Medically Significant AE List.

Blood and lymphatic System
 
Bone marrow failure
 
Disseminated Intravascular Coagulation
 
Haemolytic anaemia
 
Thrombotic Thrombocytopenic Purpura
	
Immune system
 
Anaphylaxis
 
Progressive multifocal leukoencephalopathy (PML)
 
Transplant rejection

Cardiovascular System
 
Cardiac arrest
 
Cardiac failure
 
Cardiomyopathy acute
 
Malignant hypertension
 
Myocardial infarction
 
Ventricular arrhythmias
	
Nervous System
 
Cerebrovascular accident
 
Coma
 
Convulsive seizures
 
Hyperthermia malignant
 
Macular oedema
 
Meningoencephalitis
 
Neuroleptic malignant syndrome
 
Suicidal behaviour

Endocrine System
 
Adrenal crisis
	
Musculoskeletal System
 
Rhabdomyolysis

Gastrointestinal System
	
Respiratory System

Acute pancreatitis GI haemorrhage GI perforation GI obstruction Necrotising colitis Peritonitis	Acute respiratory failure Pulmonary hypertension Pulmonary thromboembolism
Hepatobiliary System Acute hepatic failure Fulminant hepatitis	Reproductive System Abortion Uterine perforation
Urinary System Acute renal failure	Skin and subcutaneous tissue Toxic epidermal necrolysis Stevens-Johnson syndrome

Medical and scientific judgement should be exercised in deciding whether other situations should be considered serious, such as important medical events that might not be immediately life-threatening or result in death or hospitalisation but might jeopardise the patient or might require intervention to prevent one of the other outcomes listed above. Examples of such events are intensive treatment in an emergency room or at home for allergic bronchospasm, blood dyscrasias or convulsions that do not result in hospitalisation, or development of dependency or abuse.

Any suspected transmission of an infectious agent via a medicinal product is considered a serious adverse reaction.

